# Supplier(s)

Celgene Corporation will supply ISTODAX® (romidepsin) to study participants at no charge.

#### 5.2.3 DRUGS DISPENSATION AND ACCOUNTABILITY

The clinical trial supplies of romidepsin will be provided in a dual pack containing one vial of romidepsin for injection and one vial of diluent. The drug vial will contain a lyophilized powder of 10 mg of lyophilized romidepsin and 20 mg of povidone, USP (used as a bulking agent). The diluent vial will contain 2 mL of a 4:1 mixture of propylene glycol and ethanol. Appropriately trained personnel using an aseptic

technique should reconstitute the drug. A volume of 2 mL of diluent should be added to the lyophilized powder and swirled until contents of the vial are free from visible particles. This provides a stock solution at 5 mg/mL. The stock solution will be diluted using aseptic technique in 500 mL 0.9% Sodium Chloride Injection, USP (0.9% saline) for patients with a body surface area (BSA) ranging from 1.35 to 2.79 m² and in 1000 mL 0.9% saline for patients with a BSA of 2.8 m². Reconstituted drug in saline is compatible with PVC, EVA, and PE IV infusion bags as well as glass bottles. The vials containing the investigational product and the kits they are packaged in will be labeled according to the Good Manufacturing Practice guidelines and the local requirements

# **Special Handling Instructions**

Females of childbearing potential should not handle or administer romidepsin unless they are wearing gloves.

#### Record of Administration

Accurate records will be kept in the source documents of all drug administration (including prescribing and dosing).

#### 5.3 Carfilzomib

Carfilzomib (trade name Kyprolis®) is an analog of epoxomicin and eponemycin, a pair of related natural products that were initially discovered as antitumor agents in animals, and later shown to inhibit the chymotrypsin-like (CT-L) activity of the 20S proteasome.

Carfilzomib, atetrapeptide epoxyketone proteasome inhibitor, was FDA approved for the treatment of relapsed and refractory multiple myeloma. Carfilzomib is a potent, selective, and irreversible inhibitor of the CT-L activity of the constitutive proteasome (the form of proteasome found in most cell types) and the immunoproteasome (the form of proteasome found in many hematopoietic cells). In studies comparing carfilzomib to bortezomib, both were found to inhibit the CT-L activity of the proteasome with comparable potency [Demo 2007].

Incubation of tumor cells in culture with carfilzomib results in rapid and sustained inhibition of proteasome activity, accumulation of polyubiquitinated proteins, and induction of apoptosis [Demo 2007]. The period of time required to induce apoptosis varies among tumor cell types and is a function of the depth and duration of proteasome inhibition, with cells derived from hematological tumors being the most sensitive to brief periods of proteasome inhibition.

The molecular formula of carfilzomib is  $C_{40}H_{57}N_5O_7$  and its molecular weight is 719.9. It's chemical name is (2S)-N-((S)-1-((S)-4-methyl-1-((R)-2-methyloxiran-2-yl)-1-oxopentan-2-ylcarbamoyl)-2-phenylethyl)-2-((S)-2-(2-morpholinoacetamido)-4-phenylbutanamido)-4-methylpentanamide..

Intravenous administration of carfilzomib in humans over 2 to 10 minutes results in suppression of proteasome CT-L activity when measured in blood 1 hour after the first dose. Inhibition of proteasome CT-L activity was comparable in whole blood and PBMCs. Proteasome inhibition was maintained in whole blood following the first dose of carfilzomib for each week of dosing, with 30-minute and bolus infusions.

#### 5.3.1 Pharmacokinetic Parameters

Following intravenous administration of doses ≥ 15 mg/m2, carfilzomib was rapidly cleared from the systemic circulation with a half-life of ≤ 1 hour on Day 1 of Cycle 1. The systemic clearance ranged from 151 to 263 L/hour, and exceeded hepatic blood flow, suggesting that carfilzomib was largely cleared extrahepatically. The pathways of carfilzomib elimination have not been characterized in humans. [Onyx 2013]

#### **5.3.2 Dose Administration**

- Carfilzomib will be diluted in 100 mL D5W and administered over approximately 30 minutes.
- The dose is calculated using the patient"s actual body surface area (BSA) at baseline. Patients with a BSA greater than 2.2 m^2 should receive a dose based upon a BSA of 2.2 m^2. Dose adjustments do not need to be made for weight changes of less than or equal to 10%. Carfilzomib may be rounded according to local institutional rounding guidelines.
- Prior to each dose of carfilzomib in Cycle 1, give 250 IV normal saline or other appropriate IV fluid before and after carfilzomib administration. At the discretion of the treating physician, give an additional 250 mL to 500 mL of IV fluids as needed following carfilzomib administration. Fluids associated with Romidepsin infusion count toward the 250 mL to 500 mL total volume and may be used as prehydration for carfilzomib. Continue IV hydration, as needed, in subsequent cycles. In patients with chronic kidney disease or history of congestive heart failure, one may consider holding hydration in addition to the romidepsin volume.

- With cycle 1, pre-medicate with dexamethasone 4 mg PO or IV prior to all doses of carfilzomib. Additionally, if dose escalating, please also plan to premedicate with dexamethasone 4mg PO or IV to reduce the incidence and severity of infusion reactions. Reinstate dexamethasone premedication (4 mg PO or IV) if these symptoms develop or reappear during subsequent cycles. Dexamethasone premedication dosing has been increased to 8 mg PO or IV in clinical trials where the carfilzomib dose has exceeded 45 mg/m².
- It is preferred that carfilzomib is given after romidepsin.
- The Initial dose of carfilzomib given to any given patient (cycle 1, day 1) will be 20mg/m^2 regardless of the dose level. Subsequent doses will be based on the patient dose level.

# 5.3.3 Storage and Handling

Carfilzomib for Injection is supplied as single-use vials containing a dose of 60 mg of carfilzomib as a white to off-white lyophilized cake or powder. Carfilzomib vials contain no antimicrobial preservatives and are intended only for single use.

Unopened vials of carfilzomib are stable until the date indicated on the package when stored in the original package at 2°C to 8°C (36°F to 46°F). Retain carfilzomib in the original package to protect from light. The reconstituted solution contains carfilzomib at a concentration of 2 mg/mL.

# 5.3.4 Supplier

Onyx will supply carfilzomib to patients at no additional charge.

# 5.3.5 DRUGS DISPENSATION AND ACCOUNTABILITY

# **Special Handling Instructions**

Females of childbearing potential should not handle or administer carfilzomib unless they are wearing gloves.

# Record of Administration/Accountability

Accurate records will be kept in the source documents of all drug administration (including prescribing and dosing).

Each site will also maintain records of each shipment of investigational product. The records will document shipment dates, method of shipment, batch numbers, and quantity of vials contained in the shipment. Upon receipt of the investigational product, the designated recipient at the study site will inspect the shipment, verify the number and condition of the vials, and prepare an inventory or drug accountability record.

Empty and partially used vials should be accounted for and destroyed at the study site in accordance with the internal standard operating procedures. Drug destruction records must be readily available for inspection by representatives of Onyx and by regulatory authorities.

Only sites that cannot destroy unused drug on-site will be required to return their unused supply of investigational product.

# 6.1 CRITERIA FOR SUBJECT ELIGIBILITY

# 6.2 Subject Inclusion Criteria

- a) Pathologically confirmed B- or T-cell lymphomas at the enrolling institution, including stage ≥ lb CTCL, which has relapsed or progressed after at least one systemic therapy.
  - Hodgkin lymphoma is allowed and will be classified as a B-cell lymphoma in the phase IIA portion.
- b) Age ≥ 18,
- c) Previous systemic anti-cancer therapy must have been discontinued at least 3 weeks prior to treatment and adverse effects must have resolved to ≤Grade 1 or baseline. In the phase Ila portion, in progressing subjects a 2 week washout may be allowed after discussion with the MSK Principal Investigator.
- d) Previous radiation, hormonal therapy, and/or surgery must have been discontinued or completed at least 2 weeks prior to treatment in this study and adverse effects must have resolved. Lymph node or other diagnostic biopsies within 2 weeks are not considered exclusionary.
- e) ECOG≤2
- f) Meet the following laboratory criteria:
  - Absolute neutrophil count ≥ 1.0/mm³,
  - Platelet count ≥ 80 K/μ (in the Phase IIa portion, if thrombocytopenia is due to bone marrow involvement platelet count must be ≥ 50 K/μL),
  - Phase Ib subjects must have calculated creatinine clearance ≥ 50ml/min by Cockcroft-Gault formula, phase IIa subjects must have calculated creatinine clearance ≥ 40ml4/min by Cockcroft-Gault formula.
  - Total bilirubin ≤ 1.5 x upper limit of normal (ULN). AST (SGOT) and ALT (SGPT) ≤ 3 x ULN.
- g) Measurable disease for phase IIa portion only.
  - Lymphoma (includes CTCL patients who are without evidence of the disease in the skin): CT or PET/CT by modified Cheson criteria with incorporation of PET.
  - CTCL: mSWAT >0, or absolute Sezary count ≥ 1000 cells/μL.

- h) All study participants must be registered into the mandatory Revlimid REMS® program, and be willing and able to comply with the requirements of the REMS® program.
- i) Short course systemic corticosteroids for disease control, improvement of performance status or non-cancer indication (≤ 7 days) must have been discontinued at least 6 days prior to study treatment. Stable ongoing corticosteroid use (≥ 30 days) up to an equivalent dose of 15 mg of prednisone is permissible.
  - Topical steroids that have been used for > 3 weeks may be continued (CTCL only).
- j) Women of reproductive potential† must adhere to the scheduled pregnancy testing as required in the Revlimid REMS® program. Men must agree to use a latex condom during sexual contact with a FCBP even if they have had a successful vasectomy. See Appendix A: Risks of Fetal Exposure, Pregnancy Testing Guidelines and Acceptable Birth Control Methods.
  - † A female of reproductive potential is a sexually mature female who:
    - has not undergone a hysterectomy or bilateral oophorectomy; or
      has not been naturally postmenopausal for at least 24 consecutive
      months (i.e. has had menses at any time in the preceding 24
      consecutive months).

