# 12.1 CRITERIA FOR THERAPEUTIC RESPONSE/OUTCOME ASSESSMENT

Response and progression of disease will be evaluated in this study using a modification of the international criteria proposed by the modified Cheson criteria with incorporation of PET/CT. [Cheson B, 2007]. The imaging modality for evaluation will be dependent on disease subtype. For aggressive lymphomas (e.g. DLBCL, PTCL, HL), PET/CT will be used for evaluation of response. For indolent lymphomas, CT alone or PET/CT may be used at the discretion of the treating physician. For CTCL, please see Section 12.0.2.

Measurable disease: Measurable lesions are defined as those that can be accurately measured in at least one dimension (longest diameter to be recorded) as  $\geq$  15 mm with conventional techniques (PET, CT, MRI, x-ray). All tumor measurements must be recorded in millimeters (or decimal fractions of centimeters).

Non-measurable disease: All other lesions (or sites of disease), including small lesions (longest diameter < 15 mm), are considered non-measurable disease. Bone lesions, leptomeningeal disease, ascites, pleural/pericardial effusions, lymphoma

Memorial Sloan Kettering Cancer Center IRB Number: 14-179 A(6)
Approval date: 12-Dec-2017

Administrative Update 1 : 06-Dec-2018

cutis/pulmonis, inflammatory breast disease, abdominal masses (not followed by CT or MRI), and cystic lesions are all non-measurable.

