# 12.1.2 Cutaneous T-cell Lymphoma (CTCL) Response Criteria

Dermatologic responses will be determined by the modified Severity-Weighted Assessment Tool (mSWAT), a standardized approach to measuring the extent and severity of overall skin disease in patients with CTCL. It will be briefly described and full details are provided in Appendix D. The purpose of this description is to optimize intra-observer objectivity and to minimize the potential for intra-observer and inter-observer variability in the measurement of overall skin disease. Only physicians who received training will be permitted to conduct mSWAT assessments during the clinical study. It is essential that physicians adhere as closely as possible to the prescribed procedures so as to reduce measurement error and variability. All efficacy assessments should be performed by the same physician for each patient whenever possible. Physicians will be instructed not to examine previous mSWAT assessments and full body photographs prior to conducting the current mSWAT assessment.

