#### 3. Calculating Skin Scores

The sum of %TBSA by lesion is derived by summing the %TBSA from all regions affected by the lesion. The sum of %TBSA across lesion types (patches, plaques and tumors) within each region cannot exceed the %TBSA for the region. For example, the %TBSA for the head region is 7%. The sum of %TBSA across lesion types from head can only range from 0-7%. The skin score subtotal by lesion type are derived by multiplying the sum of %TBSA for patches from all regions by 1, sum of %TBS of plaques from all regions by 2, and the sum of %TBSA of tumors or ulcers from all regions by 4. The skin score total is derived from summing the skin score subtotals for patches, plaques and tumors or ulcers. The skin score total is dimensionless with a scale of 0 to 400.

Region	% TBSA for the region	% TBSA Patch (or flat erythema)	% TBSA Plaque (or elevated/indurated erythema)	% TBSA Tumor/ Ulceration (or erythema w/fissuring, ulceration)
Head	7			
Neck	2			
Anterior Trunk	13			
Posterior Trunk	13			
Buttocks	5			
Genitalia	1			
Upper Arms	8			
Forearms	6			
Hands	5			
Thighs	19			
Lower Leg	14			
Feet	7			
% BSA by category	100			
Severity Weighting Factor		X 1	X 2	X 4
Skin Score Subtotal				

Responses will be determined by the criteria described in the table below. Progression of disease while on treatment should be confirmed by a second assessment 1-4 weeks later so that patients who experience a temporary flare of disease due to skin infection or other intercurrent illnesses are not removed from the study prematurely.

Assessment	Description	Status
Completely clear	No evidence of disease; 100% improvement	CR
Marked Improvement	Greater than or equal to 50% decrease in skin scores compared	PR
Slight Improvement	Less than 50% decrease in skin scores compared to baseline	SD
Worse	≥ 25% increase in skin scores compared to baseline while the patient is actively taking the study drug or ≥ 50% increase in the sum of the products of the greatest diameters of pathologically positive lymph nodes (should be documented by biopsy) compared to baseline while the patent is actively taking the study drug.	PD

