Baseline disease assessments must be performed after discontinuation of most recent anti-cancer therapy including systemic steroids. Outside scans are acceptable if performed within 28 days.

 The imaging modality for evaluation will be dependent on disease subtype. For aggressi ve lymphomas (e.g. DLBCL, PTCL, HL), PET/CT will be used for evaluation of response. For indolent lymphomas, CT alone or PET/CT may be used at the discretion of the treating physician. A bone marrow will only be repeated to confirm a complete response if previously known to be involved. Cutaneous T-cell lymphoma patients (CTCL) will have an mSWAT (Appendix D) performed at these time points and imaging at baseline. In CTCL patient's, imaging will be repeated if appropriate (patients with known nodal or visceral disease) every other cycle. Sezary panel in patients with Sezary syndrome. Cutaneous lymphoma patients without nodal or visceral disease will have imaging repeated only to confirm a complete response.

 An additional safety assessment will be done 28 days (+/- 7 days) following the last dose of protocol therapy.

Response assessment will be performed at the end of cycles 2. Thereafter, response assessment will occur at the end of every third cycle (5.8,11, etc..) until disease progression or removal from study.

10 +/- 3 days

if not performed within 28 days

For cycle 3 and beyond, laboratory assessments performed up to three days prior to the day of treatment are adequate for treatment as long as they are within the treatment parameters.

 For cycles 2, 3 and 4, concomitant medications and adverse events may be performed via an assessment by telephone +/- 3 days of day 15 of the cycle. Beyond cycle 4, day 15 assessments are not required.  5 days to + 3 days.

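### A CTCL patient can qualify as measurable on a Sezary count alone, but the CTCL response table has no blood term for PR, SD or PD and no rule for combining skin and blood

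*Combined protocol and SAP*

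**What the plan says.** Section 6.2 item g requires measurable disease in phase IIa and offers two routes. The imaging route reads "Lymphoma (includes CTCL patients who are without evidence of the disease in the skin): CT or PET/CT by modified Cheson criteria with incorporation of PET". The CTCL route reads "mSWAT >0, or absolute Sezary count ≥ 1000" cells/µL. The two parts of the CTCL route are alternatives, so the count suffices without skin disease.

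For response, Section 12.1 sends these patients elsewhere: "For CTCL, please see Section 12.0.2" (the section now headed 12.1.2). That section says "Dermatologic responses will be determined by the modified Severity-Weighted Assessment Tool (mSWAT", and refers to Appendix D for details. The Appendix D table gives:

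- CR: "No evidence of disease; 100% improvement"
- PR: "Greater than or equal to 50% decrease in skin scores compared" (taken here as compared with baseline, as in the other rows)
- SD: a smaller fall in the same score
- PD: "≥ 25% increase in skin scores compared to baseline while the patient is actively taking the study drug", or at least a 50% increase in the summed products of pathologically positive nodes

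Blood is measured. Section 8.2 lists a Sezary panel at screening, for Sezary syndrome only, described by its flow-cytometry markers. Footnote 7 of Appendix G, attached to the disease/response row, adds "Sezary panel in patients with Sezary syndrome" with no threshold and no stated use.

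**The concern.** Eligibility treats blood as a disease site that can stand alone, and Section 3.3 lists blood among the sites where romidepsin was active. The response table does not carry blood through. Two kinds of patient are affected. One has only blood disease and has no baseline skin score from which a response can be measured. The other has skin and blood disease moving in opposite directions and is classified on skin alone.

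ORR counts best responses of CR/CRu or PR, and DOR and EFS use the date of progression (Section 4.2, Design). An unscorable or one-sided classification therefore reaches all three. If no rule is written beforehand, each such case will be settled individually, possibly after the results are known.

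**Working it through.** **Inputs.** Regional skin weights, severity weights and response rows: Appendix D. Measurable-disease rule: Section 6.2 item g. Extracutaneous criteria: Section 12.1.1. Endpoint definitions: Section 4.2. Cohort sizes, 10 B-cell and 10 T-cell for a total of 20: the phase IIa treatment plan in Section 9.3. The number k of affected patients is not given; k = 1 to 3 is an assumption.

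**Step 1: what the skin score contains.** The 12 regional weights sum to 7 + 2 + 13 + 13 + 5 + 1 + 8 + 6 + 5 + 19 + 14 + 7 = 100. With severity weights of 1, 2 and 4, the score runs from 0 to 100 × 4 = 400, which reproduces the plan's stated scale. Every term is skin area; none is blood.

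**Step 2: blood-only patient.** Percent change is 100 × (S_t − S_0)/S_0, where S_0 is the baseline score and S_t the score at assessment. With S_0 = 0 the denominator is zero, so the 50% fall (PR), the smaller fall (SD) and the 25% rise (PD) are all undefined. The nodal part of PD needs nodes. In Section 12.1.1, PR is a fall of at least 50% in the nodal products, and PD is nodal growth or a new lesion. With no imageable disease there is nothing to measure for PR, and a Sezary count rising from 1000 to any value meets no PD criterion. A new lesion elsewhere might still be called PD, but the blood disease cannot be.

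**Step 3: discordant patient.** Suppose the skin score falls from S_0 to 0.5 × S_0 and the Sezary count rises. The PR row is met. No PD row is met, because no row mentions blood. The patient is PR, and DOR starts. Conversely, blood that clears while the skin score is unchanged is not PR.

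**Step 4: when blood progression becomes an event.** Section 4.2 ends DOR and EFS at progression, change of therapy or death, and DOR also at last contact. Blood progression is not a written progression event, so it enters only at the later change of therapy or death.

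**Step 5: effect on ORR.** The largest shift is 100 × k/n points. If the k patients count as non-responders, the highest attainable ORR is (n − k)/n.

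| Assumed k | T-cell shift, n = 10 | T-cell maximum ORR | Pooled shift, n = 20 | Pooled maximum ORR |
|---|---|---|---|---|
| 1 | 10 points | 90% | 5 points | 95% |
| 2 | 20 points | 80% | 10 points | 90% |
| 3 | 30 points | 70% | 15 points | 85% |

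For scale, Section 14.0 promises confidence intervals without giving a level or method. Assuming exact 95% limits, 5/10 gives 18.7% to 81.3% and 4/10 gives 12.2% to 73.8%. One reclassified patient moves the estimate well within that uncertainty.

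**The case against.** Two stronger readings are tempting. A reader might infer that a blood-only patient cannot respond at all. The documents do not support that: the CR row, "No evidence of disease; 100% improvement", is not worded as a skin-score criterion, and CR in Section 12.1.1 is also framed generally. Clearance on the panel could be argued to be CR, and CR counts toward ORR. A reader might also infer that blood progression is ignored. It is not lost if it leads to new treatment or death, since both end DOR and EFS. The fault is that it is dated late.

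Other points also carry weight. The panel belongs to the disease/response row, Section 12.1.2 confines the skin tool to dermatologic response, and Section 16.1.2 lets the response review committee obtain further laboratory reports. Blood data may therefore be in front of the reviewers. The strictly blood-only case is narrow: CTCL, a skin score of exactly 0, a qualifying count and no imageable disease. The T-cell cohort has no CTCL quota. Efficacy is secondary and descriptive, and the only stopping rule concerns DLTs.

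These points limit the consequences. They do not supply a blood threshold for PR, SD or PD, or a rule for combining skin and blood, and no other section does.

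**Conclusion.** The mismatch is real. Eligibility admits blood disease as measurable, while the CTCL table leaves PR undefined for a blood-only patient and has no PD criterion for blood disease. It also awards PR on skin improvement whatever the blood is doing. The effect is at most 10 points on T-cell ORR and 5 points on pooled ORR per patient, with later progression dates for DOR and EFS. This is a per-patient bound and not a forecast, because the number of Sezary patients is unknown. The conclusion assumes that the Appendix D table is applied as written and that the committee has no separate written blood rule. The primary safety objective is untouched.

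**What to change.** Reconcile Section 6.2 item g, Section 12.1.2, the Appendix D table and footnote 7 of Appendix G before response review begins. For patients with blood involvement at baseline:

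- Add blood response and progression categories to Appendix D, based on the Sezary panel.
- Record the absolute count at each response assessment, and state the timing.
- Add a rule that overall PR requires no progression in any involved compartment.

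The clinical team should set the thresholds. Removing the Sezary count as a stand-alone qualifier would be simpler, but it solves only the blood-only case and leaves discordant skin and blood results unresolved.

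The cost is a short table and a few lines of text. Some skin-only responses may be reclassified. The panel is currently limited to Sezary syndrome and described by markers, so reporting of the absolute count has to be specified. Restricting the rule to patients with blood involvement at baseline limits any added testing.
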